Appendix 1: Schedule of Activities (cont.)

- ^f Medical history, including clinically significant diseases, surgeries, cancer history (including prior cancer therapies and procedures) and *EGFR* and *ALK* mutational status, reproductive status, smoking history, and use of alcohol and drugs of abuse, will be recorded at baseline. In addition, all medications (e.g., prescription drugs, over-the-counter drugs, vaccines, herbal or homeopathic remedies, nutritional supplements) used by the patient within 7 days prior to initiation of study treatment will be recorded. At the time of each follow-up physical examination, an interval medical history should be obtained and any changes in medications and allergies should be recorded (see Section 4.5.2).
- ^g For patients with non-squamous NSCLC who have unknown *EGFR* or *ALK* status will be required to be tested at prescreening or screening. Patients with squamous NSCLC who have an unknown *EGFR* or *ALK* status are eligible and will not be required to be tested at prescreening or screening. *EGFR* and/or *ALK* status may be assessed locally or at a central laboratory. *EGFR* status assessed locally can be performed on tissue or cytology using a validated health authority approved test that detects mutations in exons 18–21 testing. If samples are submitted for central *EGFR* and/or *ALK* testing, [REDACTED]
- ^h Vital signs include pulse rate, respiratory rate, blood pressure, and temperature. Vital signs should be recorded as described in Section 4.5.4.
- ⁱ For patients in either arm at participating sites who have provided written informed consent to participate in mobile nursing visits, this assessment or procedure may be performed by a trained nursing professional at the patient's home or another suitable location.
- ^j Complete and limited physical examinations are defined in Section 4.5.3.
- ^k ECOG Performance Status, a limited physical examination, and local laboratory assessments may be performed ≤ 96 hours before Day 1 of each cycle. Local laboratory assessments may be performed ≤ 96 hours before Day 15 of each cycle.
- ^l An ECG is required at screening, at the treatment discontinuation/completion visit, and when clinically indicated. ECGs for each patient should be obtained from the same machine wherever possible. Lead placement should be as consistent as possible. ECG recordings must be performed after the patient has been resting in a supine position for at least 10 minutes.
- ^m Hematology consists of WBC count, RBC count, hemoglobin, hematocrit, platelet count, and differential count (neutrophils, eosinophils, basophils, monocytes, and lymphocytes).
- ⁿ At screening, patients must have adequate hematologic and end-organ function defined by laboratory results obtained within 14 days prior to initiation of study treatment (Day 1 of Cycle 1), as described in Section 4.1.1.
- ^o Chemistry panel (serum or plasma) includes bicarbonate or total carbon dioxide (if considered standard of care for the region), sodium, potassium, magnesium, chloride, glucose, BUN or urea, creatinine, total protein, albumin, phosphate, calcium, total bilirubin, ALP, ALT, AST, and LDH.
- ^p All women of childbearing potential (including those who have had a tubal ligation) must have a serum pregnancy test performed at screening and documented as negative within 14 days prior to initiation of study treatment (Day 1 of Cycle 1). During the study, urine pregnancy tests will be performed on Day 1 of every cycle. After study treatment discontinuation, a urine pregnancy test will be performed at either 90 days after the final dose of tiragolumab, 5 months after the final dose of atezolizumab, or 3 months after the final dose of durvalumab, whichever is later. If a urine pregnancy test is positive, it must be confirmed by a serum pregnancy test.

Appendix 1: Schedule of Activities (cont.)

^q TSH, free T3 (or total T3 at sites where free T3 is not performed), and free T4 will be collected at screening, on Day 1 of Cycles 1 and 4, every fourth cycle thereafter (e.g., Cycles 1, 4, 8, and 12), and at the treatment discontinuation/completion visit.

^s Urinalysis by dipstick (specific gravity, pH, glucose, protein, ketones, and blood). Urinalysis is required at screening and will be obtained when clinically indicated.

^t A CT scan with contrast or MRI scan with contrast of the head must be performed at screening to evaluate CNS metastasis in all patients. If a CT scan with contrast is performed and the presence of brain metastases is considered equivocal, an MRI scan of the head is required to confirm or refute the diagnosis of CNS metastases at baseline. Patients with CNS metastases are not eligible for the study (see Section 4.1.2).

^u MRI scans with contrast of the chest, abdomen, and pelvis with a non-contrast CT scan of the chest may be used in patients for whom CT scans with contrast are contraindicated (i.e., patients with contrast allergy or impaired renal clearance)

^v Durvalumab will be administered by continuous IV infusion on Days 1 and 15 (for patients on Q2W dosing) over 60 minutes. Dosing of durvalumab will occur only if the clinical assessment and local laboratory test results are acceptable. If a tumor assessment was performed, results must be reviewed by the investigator before dosing of study treatment.

^w Atezolizumab will be administered prior to tiragolumab by continuous IV infusion on Day 1 of each 28-day cycle. For atezolizumab, the initial dose will be delivered over 60 (\pm 15) minutes. If the first infusion is well tolerated, all subsequent infusions may be delivered over 30 (\pm 10) minutes. Following atezolizumab, patients will receive tiragolumab by continuous IV infusion every 28 days on Day 1 of each 28-day cycle as indicated. For tiragolumab, the initial dose will be delivered over [REDACTED] minutes. If the first infusion is well tolerated, all subsequent infusions may be delivered over [REDACTED] minutes. Dosing of both study drugs will occur only if the clinical assessment and local laboratory test results are acceptable. If a tumor assessment was performed, results must be reviewed by the investigator before dosing of study treatment.

^x Concomitant medications include any prescription medications, over-the-counter medications, vaccines, herbal or homeopathic remedies, or nutritional supplements. Any medications the patient has used within the 7 days prior to the initiation of study treatment should be documented. At subsequent visits, changes to current medications or medications used since the last documentation will be recorded.

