4.3.2.1 Atezolizumab

Patients in the experimental arm will receive 1680 mg atezolizumab at a fixed dose administered by IV infusion on Day 1 of each 28-day cycle (see Section [3.4.6](#)). The atezolizumab dose is fixed and is not dependent on body weight.

Atezolizumab infusions will be administered per the instructions outlined in [Table 3](#).

No dose modification for atezolizumab is allowed. Guidelines for treatment interruption or discontinuation are provided in [Appendix 10](#). Guidance on study drug administration in the context of management of specific adverse events is provided in [Section 5.1.5](#).

For further details on dose preparation, storage, and administration instructions for atezolizumab, refer to the pharmacy manual and/or the Atezolizumab Investigator's Brochure.

Table 3 Administration of First and Subsequent Infusions of Atezolizumab

| | Day 1, Cycle 1 Infusion | Day 1 Infusion of Subsequent Cycles |
|--|---|--|
| Atezolizumab infusion | 
 No premedication is permitted prior to the atezolizumab infusion. Vital signs (pulse rate, respiratory rate, blood pressure, and temperature) should be recorded within 60 minutes prior to the infusion. Atezolizumab should be infused over 60 (\pm 15) minutes. If clinically indicated, vital signs should be recorded every 15 (\pm 5) minutes during the infusion. | 
 If the patient experienced an IRR with any previous infusion of atezolizumab, premedication with an antihistamine and/or antipyretic medication may be administered for subsequent doses at the discretion of the investigator. Vital signs should be recorded within 60 minutes prior to the infusion. Atezolizumab should be infused over 30 (\pm 10) minutes if the previous infusion was tolerated without an IRR or 60 (\pm 15) minutes if the patient experienced an IRR with the previous infusion. If clinically indicated, vital signs should be recorded during the infusion. |

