| Observation period after atezolizumab infusion | 
 After the infusion of atezolizumab, the patient begins a 60-minute observation period. Vital signs should be recorded at 30 (\pm 10) minutes after the infusion of atezolizumab. Patients will be informed about the possibility of delayed post-infusion symptoms and instructed to contact their study physician if they develop such symptoms. | 
 If the patient tolerated the previous atezolizumab infusion well without infusion-associated adverse events, the observation period after the next and following infusions may be reduced to 30 minutes. If the patient experienced infusion-associated adverse events in the previous infusion, the observation period should be 60 minutes. If clinically indicated, vital signs should be recorded at 30 (\pm 10) minutes after the infusion of atezolizumab. |

IRR = infusion-related reaction.

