4.3.2.2 Tiragolumab

Following the administration of atezolizumab and an observation period (see [Table 3](#)), patients in the experimental arm will receive 840 mg tiragolumab at a fixed dose

administered by IV infusion on Day 1 of each 28-day cycle (see Section 3.4.6). The tiragolumab dose is fixed and is not dependent on body weight.

Tiragolumab infusions will be administered per the instructions outlined in Table 4.

No dose modification for tiragolumab is allowed. Guidelines for treatment interruption or discontinuation are provided in Section 4.6.1. Guidance on study drug administration in the context of management of specific adverse events is provided in Section 5.1.5.

For further details on dose preparation, storage, and administration instructions for tiragolumab, refer to the pharmacy manual and/or the Tiragolumab Investigator's Brochure.

Table 4 Administration of First and Subsequent Infusions of Tiragolumab

| | Day 1, Cycle 1 Infusion | Day 1 Infusion of Subsequent Cycles |
|--|--|---|
| Infusion of tiragolumab | 
 No premedication is permitted prior to the tiragolumab infusion. Vital signs (pulse rate, respiratory rate, blood pressure, and temperature) should be recorded within [REDACTED] minutes prior to the infusion. Tiragolumab should be infused over [REDACTED] minutes. Vital signs should be recorded every [REDACTED] minutes during the infusion. | 
 If the patient experienced an IRR during any previous infusion of tiragolumab, [REDACTED] may be administered for subsequent doses, at the discretion of the investigator. Vital signs should be recorded within [REDACTED] minutes prior to the tiragolumab infusion. Tiragolumab should be infused over [REDACTED] minutes if the previous infusion was tolerated without an infusion-related reaction, or [REDACTED] minutes if the patient experienced an infusion-related reaction with the previous infusion. Vital signs should be recorded during the infusion if clinically indicated. |

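### Minor inconsistency: Appendix 1 footnote w lets a well-tolerated first infusion license shorter infusions thereafter, while Tables 3 and 4 decide by the previous infusion

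*Protocol*

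**What the plan says.** Three places in the protocol deal with how long infusions after the first should take.

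- **Appendix 1, footnote w.** The first atezolizumab dose runs over 60 (±15) minutes. Then: "If the first infusion is well tolerated, all subsequent infusions may be delivered over 30" (±10) minutes. Tiragolumab gets a sentence with the same first-infusion condition and redacted minutes. The footnote does not mention a return to the longer duration after a later reaction and does not refer to Table 3 or Table 4.
- **Section 4.3.2.1 and Table 3 (atezolizumab).** The section makes the table the operative text: "Atezolizumab infusions will be administered per the instructions outlined in" Table 3. For cycles after the first, the table has two durations. The shorter is 30 minutes, with a tolerance of 10, and applies when the last dose caused no reaction. The longer is 60 minutes, with a tolerance of 15, and its condition reads: "minutes if the patient experienced an IRR with the previous infusion".
- **Section 4.3.2.2 and Table 4 (tiragolumab).** "Tiragolumab infusions will be administered per the instructions outlined in Table 4". That table gives one redacted duration, "minutes if the previous infusion was tolerated without an infusion-related reaction, or" another redacted duration, "minutes if the patient experienced an infusion-related reaction with the previous infusion".

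Section 5.1.1.1, which covers tiragolumab only, also ties shortening to the preceding infusion and sends the reader to Section 4.3.2.

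**The concern.** The footnote and the tables use different triggers for the same decision. The tables look back one dose every time. The footnote looks back to Cycle 1 once and then releases all later doses. Footnote w is the outlier among these texts.

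At stake is one safeguard at one kind of dose. IRRs are a listed risk of atezolizumab (Section 5.1.2), and Appendix 10 records them with both drugs. The sponsor's own rule in Table 3 is to go back to the longer infusion after a reaction. A coordinator working from the Schedule of Activities could read footnote w as allowing the short infusion at exactly that dose.

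There is also a compliance consequence. Section 4.3.2 has infusion start and stop times recorded on the eCRF, and Section 9.2 requires deviations to be documented and explained. A 30-minute atezolizumab infusion straight after a later IRR is allowed by footnote w and departs from Table 3, so whoever reviews that record has two standards to apply.

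**Working it through.** The plan gives no figure to reproduce. The check sets the two rules side by side and works through the possible patient histories, reading *well tolerated* as *without an IRR*.

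**Inputs**

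| Item | Value | Source |
|---|---|---|
| Maximum number of cycles | 13 | Section 3.1.1 |
| Footnote w, later atezolizumab doses if Cycle 1 well tolerated | 30 (±10) min permitted | Appendix 1, footnote w |
| Table 3, previous atezolizumab infusion without IRR | 30 (±10) min | Section 4.3.2.1 |
| Table 3, previous atezolizumab infusion with IRR | 60 (±15) min | Section 4.3.2.1 |
| Tiragolumab durations | redacted; triggers legible | Table 4 and footnote w |

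**Comparison by history (atezolizumab)**

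| History | Footnote w | Table 3 | Conflict? |
|---|---|---|---|
| No IRR at any cycle | 30 min permitted | 30 min | No |
| Cycle 1 well tolerated, IRR at Cycle k (k = 2 to 12), dosed again at Cycle k+1 | 30 min still permitted | 60 min | **Yes, at Cycle k+1** |
| Cycle 1 well tolerated, IRR at Cycle 13 | no later dose | no later dose | No |
| Cycle 1 not well tolerated | condition not met; silent | decided by the previous infusion | No |

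**Size of the conflict at Cycle k+1**

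- Window permitted by footnote w: 30 − 10 to 30 + 10 = 20 to 40 min.
- Window in Table 3 after an IRR: 60 − 15 to 60 + 15 = 45 to 75 min.
- Gap between the windows: 45 − 40 = 5 min, so they do not overlap.
- Nominal difference: 60 − 30 = 30 min.

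Each IRR at Cycles 2 to 12 that follows a well-tolerated Cycle 1, and is itself followed by another dose, gives one dose at which the texts disagree. If the infusion at Cycle k+1 passes without a reaction, the rules agree again from Cycle k+2. The 30-minute duration is Table 3's own duration after a tolerated infusion. The mismatch is therefore about when that duration may be used, not about the duration itself.

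**Tiragolumab.** The triggers differ in the same way (first infusion against previous infusion). With the minutes redacted, the size of the difference cannot be computed.

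**The case against.** The strongest answer is that the body text already settles the matter. Sections 4.3.2.1 and 4.3.2.2 state that infusions will follow Tables 3 and 4, and footnote w only says that later infusions *may* be shortened. A site that follows the tables complies with both texts. Table 3's other provisions after a reaction also stand untouched: discretionary premedication after any previous atezolizumab IRR, and an observation period that may be cut to 30 minutes only "If the patient tolerated the previous atezolizumab infusion well without infusion-associated adverse events".

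Most of this stands, and it is why the point is minor. It does not remove the conflict. Section 4.5 gives Appendix 1 as the schedule of activities to be performed. Footnote w states durations itself, whereas footnotes h, j and n of the same appendix send the reader to the body section. No visible clause says which text prevails. A permission that Table 3 withholds is still a discrepancy.

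A second answer is that redosing after an IRR may be controlled elsewhere. The management entries for IRRs in Appendix 10 Table 7 are redacted, as is the sentence after the Cycle 1 guidance there, and the pharmacy manual is not among the documents. This also stands: the conflict arises only if the patient is dosed again, and further controls cannot be judged.

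Three stronger readings are tempting but not supported.

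- *That the texts conflict in both directions.* After an IRR at Cycle 1 and a tolerated Cycle 2, Table 3 calls for 30 minutes at Cycle 3. A reader might infer that footnote w forbids this, and so count up to 13 − 3 + 1 = 11 conflicting doses. But footnote w grants a permission under a condition and says nothing when the condition fails. Silence is not a rival rule.
- *That Cycle 2 also conflicts*, because a mild Cycle 1 IRR could be called well tolerated. The visible text leaves the phrase undefined, but nothing in it suggests this use. The observation row of Table 3 pairs tolerating an infusion well with the absence of infusion-associated adverse events.
- *That patients will have more IRRs, or that efficacy results are affected.* The visible text gives no IRR rate, and no visible analysis in the SAP uses infusion duration.

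**Conclusion.** Footnote w is wrong as written, at low severity. It is an internal inconsistency, not a design decision: nothing suggests that the sponsor meant to depart from its own tables.

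The conflict runs in one direction only. After a well-tolerated Cycle 1 and an IRR at a later cycle, the next atezolizumab infusion may take 20–40 minutes under footnote w and should take 45–75 minutes under Table 3. Tiragolumab has the same mismatch in trigger, of unknown size.

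The conclusion assumes that the patient is dosed again after the IRR and that the redacted Appendix 10 text and the pharmacy manual do not already close the gap. The number of patients affected cannot be estimated. No endpoint, error rate or efficacy analysis is touched.

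**What to change.** At the next protocol amendment, replace the infusion-duration sentences in footnote w (initial dose and later infusions, for each drug) with: *For infusion durations, see Table 3 (Section 4.3.2.1) and Table 4 (Section 4.3.2.2).* The section numbers are needed because Appendix 10 has its own Tables 3 and 4, and Appendix 4 its own Table 3.

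Alternatively, keep the durations in the footnote, change the condition for both drugs to *if the previous infusion was tolerated without an IRR*, and leave the longer duration to apply otherwise.

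Tables 3 and 4 need no change. The cost is an edit to one footnote, with no new data, visits or procedures.

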Appendix 1: Schedule of Activities (cont.)

^y Patients will undergo tumor assessments at screening and every 8 weeks (± 7 days) for 48 weeks following Day 1 of Cycle 1 regardless of treatment delays. After completion of the Week 48 tumor assessment, tumor assessments will be required every 12 weeks (± 7 days) regardless of treatment delays until confirmed investigator-assessed radiographic disease progression as (as defined by growth of existing lesions, new lesions, or recurrence of previously resolved lesions) per RECIST v1.1, withdrawal of consent, or study termination by the Sponsor, whichever occurs first. Patients who are treated beyond disease progression per RECIST v1.1 will undergo tumor assessments at the frequency described above until treatment is discontinued. Patients who discontinue treatment for reasons other than radiographic disease progression per RECIST v1.1 (e.g., toxicity, symptomatic deterioration, completion of study treatment) will continue scheduled tumor assessments at the frequency described above until confirmed investigator-assessed radiographic disease progression per RECIST v1.1, withdrawal of consent, death, or study termination by the Sponsor, whichever occurs first. In the absence of radiographic disease progression confirmed by scan per RECIST v1.1, tumor assessments should continue regardless of whether a patient starts a new anti-cancer therapy.

If a tumor assessment shows radiographic disease progression per RECIST v1.1, and a subsequent scan confirms radiographic disease progression per RECIST v1.1, the date of disease progression is the date of the initial assessment of progression.

Existence of disease-related symptoms (cough, hemoptysis, pain, dyspnea, fatigue, cachexia, vision impairment, vertigo) will be evaluated at each tumor assessment.

^z If a tumor assessment shows disease progression, it should be confirmed pathologically and/or by unequivocal radiographic evidence from the scan. If the scan shows equivocal findings (e.g., mediastinal nodes measure < 1.5 cm in the short axis, lung parenchymal lesions or visceral lesions measuring < 1 cm in the longest diameter), a biopsy should be performed. If a biopsy is not feasible or safe, then confirmatory scans should be performed no later than the next scheduled assessment or earlier, if clinically feasible.

^{aa} The investigator's assessment of overall tumor response at all timepoints should only be based on RECIST v1.1 (see [Appendix 4](#)).

Assessments should be performed by the same evaluator if possible to ensure internal consistency across visits. Results must be reviewed by the investigator before dosing at the next cycle. Patients who discontinue treatment for reasons other than confirmed radiographic disease progression (as defined by growth of existing lesions, new lesions, or recurrence of previously resolved lesions) per RECIST v1.1 (e.g., toxicity, symptomatic deterioration) will continue scheduled tumor assessments at the frequency described above until radiographic disease progression per RECIST v1.1, withdrawal of consent, death, or study termination by Sponsor, whichever occurs first. In the absence of radiographic disease progression per RECIST v1.1, tumor assessments should continue regardless of whether a patient starts a new anti-cancer therapy. Scans will be sent to an IRF for central review.

Appendix 1: Schedule of Activities (cont.)

[figure not shown]
bb

- cc After informed consent has been obtained but prior to initiation of study treatment, only serious adverse events caused by a protocol-mandated intervention should be reported. After initiation of study treatment, all adverse events will be reported until [REDACTED] days after the final dose of study treatment or [REDACTED], and serious adverse events will continue to be reported until [REDACTED] days after the final dose of study treatment or [REDACTED]. In addition, adverse events of special interest will continue to be reported until [REDACTED] days after the final dose of study treatment, [REDACTED]. After this period, all deaths, regardless of cause, should be reported. In addition, if the investigator becomes aware of a serious adverse event that is believed to be related to prior exposure to study treatment, the adverse event should be reported. The investigator should follow each adverse event until the event has resolved to baseline grade or better, the event is assessed as stable by the investigator, the patient is lost to follow-up, or the patient withdraws consent. Every effort should be made to follow all serious adverse events considered to be related to study treatment or protocol-related procedures until a final outcome can be reported. Adverse events during the post-treatment period may be collected by telephone.
- dd Experimental arm only (e.g., patients who are receiving atezolizumab plus tiragolumab). Refer to the table in [Appendix 2](#) for details on the PK and immunogenicity collection schedule. Blood samples should be processed to obtain serum and plasma.
- ee Blood sample for biomarker is collected from patients in both arms. See [Appendix 2](#).

